DBP	Diastolic Blood Pressure
DMC	Data Monitoring Committee
ECG	Electrocardiogram
eCRF	Electronic Case Report Form
EMA	European Medicines Agency

ER	Emergency Room
E-R	Exposure-Response
EXACT-PRO	The EXAcerbations of Chronic pulmonary disease Tool-Patient Reported Outcome
FDA	Food and Drug Administration
FEV1	Forced Expiratory Volume in one second
FVC	Forced Vital Capacity
GCP	Good Clinical Practice
GOLD	Global initiative for chronic Obstructive Lung Disease
HR	Heart Rate
Hs-CRP	High-sensitivity C-Reactive Protein
IAC	Independent Adjudication Committee
ICH	International Conference on Harmonisation
ICS	Inhaled Corticosteroid
ICU	Intensive Care Unit
IL-6	interleukin-6
IMP	Investigational Medicinal Product
INR	International Normalised Ratio
IRT	Interactive Response Technology
ITT	Intention-To-Treat
IV	intravenous
kg	Kilogram
LABA	Long-Acting β 2-Agonist
LLOQ	Lower Limit of Quantification
LS	Least Square
MedDRA	Medical Dictionary for Regulatory Activities
mg	Milligram
mL	millilitre
mMRC	modified Medical Research Council
MMRM	Mixed Model for Repeated Measurements
MOV	Maximum Observed Value
MPO	Myeloperoxidase

NCS	Not Clinically Significant
OC	Observed Cases
PD	Pharmacodynamic
PFT	Pulmonary Function Test
PK	Pharmacokinetic
PoC	Proof of Concept
PP	Per-Protocol
PR	Time interval between the onset of the P wave and the beginning of the QRS complex
PRO	Patient Reported Outcome
PT	Preferred Term
QRS	Time interval between the beginning of the Q wave and the termination of the S wave
QTc	corrected QT interval of the electrocardiogram
QTcB	Bazett-corrected time interval between the Q and T waves
QTcF	Fridericia-corrected time interval between the Q and T waves
RBC	Red Blood Cell
RR	Respiratory Rate
SABA	Short-Acting β 2-Agonist
SAMA	Short-Acting Muscarinic Antagonist
SAE	Serious Adverse Event
SAP	Statistical Analysis Plan
SBP	Systolic Blood Pressure
SD	Standard Deviation
SDTM	Study Data Tabulation Model
SE	Standard Error
SI	Standard International
SoC	Standard of Care
SOC	System Organ Class
TEAE	Treatment-Emergent Adverse Event
TFLs	Tables, Figures and Listings
TNF- α	Tumour Necrosis Factor-alpha

ULN	Upper Limit Normal
ULOQ	Upper Limit of Quantification
WBC	White Blood Cell
WHO	World Health Organisation
6MWT	6-Minute Walk Test
β -HCG	Beta-Human Chorionic Gonadotropin

1 INTRODUCTION

The purpose of this Statistical Analysis Plan (SAP) is to provide detailed descriptions of the statistical methods, data derivations and data displays for study protocol No. MBCT206: A Phase IIa, two-part, randomised, multi-centre, multinational, double-blind, placebo-controlled, parallel group study to compare the efficacy and safety of BCT197 when added on to standard of care for the treatment of acute respiratory exacerbations of chronic obstructive pulmonary disease (COPD) requiring hospitalisation in adults.

This analysis plan is based on the final protocol version 1.0 dated 05 November 2015, final protocol version 2.0 (amendment 1) dated 23 December 2015, final protocol version 3.0 (amendment 2) dated 10 March 2016, final protocol version 4.0 (amendment 3) dated 26 May 2016, and final protocol version 5.0 (amendment 4) dated 08 November 2016.

A summary of the key changes to each protocol amendment is presented in Appendix A.

The table of contents and templates for the Tables, Figures and Listings (TFLs) will be produced in a separate document.

Any deviations from this SAP will be described and justified in the Clinical Study Report (CSR).

The preparation of this SAP has been based on International Conference on Harmonisation (ICH) E9¹.

All data analyses and generation of TFLs will be performed using SAS 9.4® or higher.

Note: This plan does not address the pharmacokinetic (PK)/pharmacodynamic (PD) analyses of BCT197 (nonlinear mixed effects PK/PD modelling) for this study. These analyses will be detailed in a separate analysis plan and results from the PK/PD modelling will be reported separately from the CSR.

2 STUDY OBJECTIVES

2.1 Primary objective

The primary objective is to evaluate the efficacy of two different dosing regimens of BCT197 added to standard of care (SoC) versus placebo added to SoC in the treatment of acute respiratory exacerbations of COPD that required hospitalisation by comparison of change in Forced Expiratory Volume in one second (FEV1) from baseline (pre-dose) to Day 7.

2.2 Secondary objectives

The secondary objectives are to evaluate the efficacy and tolerability of two different dosing regimens of BCT197 added to SoC versus placebo added to SoC in treatment of an acute exacerbation of COPD requiring hospitalisation by measuring the following:

Efficacy of BCT197:

1. Comparison of FEV1 on Days 3, 10, and 14
2. Normalisation evaluation of spirometry parameter (FEV1 and FEV1/FVC) response over time (performed daily from Days 1 to 7, 10, and 14, and Weeks 8, 12 and 26) compared with the most recent test performed within the last 12 months outside an exacerbation (pre-study FEV1 and FEV1/FVC value)
3. Time taken to improvement of 100 mL in FEV1 compared to Baseline versus placebo
4. Assessment of AUC of FEV1 over time among groups
5. Respiratory rate (RR) normalisation over time (performed daily from Days 1 to 7, 10 and 14) among groups
6. RR at Days 3, 7, 10, and 14 among groups
7. Time to improvement based on EXACT-PRO total score
8. Assessment of AUC of EXACT-PRO over time among groups
9. Evaluate the number of COPD-related deaths among groups
10. Evaluate the number of moderate/severe COPD exacerbations (classified according to European Medicines Agency [EMA]/Committee for Medicinal Products for Human Use [CHMP] guidelines) over time among groups
11. Evaluate time to next moderate/severe COPD exacerbation
12. Change from baseline at each inter-visit period and over the entire period of the study in the average EXACT-PRO total score and domain scores
13. Evaluate the use of rescue therapy during the study
14. Evaluate time from hospitalisation admission until subject is medically ready (COPD-related) for discharge
15. To characterize the PK of BCT197 in adults with COPD.

Safety and tolerability of BCT197:

1. Evaluation of each treatment-emergent adverse event (TEAE)/serious adverse event (SAE) (from first dose of study drug until study completion)
2. Evaluation of the incidence of pneumonia from first dose of study drug until study completion
3. TEAEs of special interest: rash, acneiform dermatitis, cervical/vaginal inflammation, headache, pruritus and liver enzymes (aspartate aminotransferase [AST], alanine aminotransferase [ALT], bilirubin)
4. Evaluation of vital signs and laboratory parameters
5. Evaluation of QTc intervals over time at Baseline, Day 1 to Day 7 (daily), Days 10 and 14
6. Quantitative sputum culture over Days 1 to 14 whenever sputum is collected for clinical purposes.

2.3 Exploratory objectives

Exploratory assessments will evaluate:

1. Exploratory composite scale endpoints comparing among the three groups at Weeks 8, 12 and 26:
 - Number of events of worsening of symptoms warranting the addition of antibiotics
 - Number of events of worsening of symptoms warranting an increase of oral dose of corticosteroids or initiation of new oral corticosteroids
 - Number of events of worsening of symptoms requiring additional treatment with oral corticosteroids and/or antibiotics after completion of the initial regimen
 - Number of events of COPD exacerbations that required re-hospitalisation
 - Number of COPD-related deaths
2. Chronic respiratory questionnaire (CRQ) at Baseline, Day 14 and at Weeks 8, 12 and 26 to evaluate recovery comparing among the three groups over time
3. Cumulative oral/IV steroid dose on Days 1 to 14, and from Day 14 to Week 26
4. Change in inflammatory blood biomarkers (IL-6, TNF- α , fibrinogen, high-sensitivity C-reactive protein [hs-CRP], and myeloperoxidase [MPO]) daily during Part 1 of the study, and at Weeks 8, 12 and 26
5. Explore the relationship between BCT197 exposure and efficacy/safety endpoints
6. Change from baseline in modified Medical Research Council (mMRC) dyspnoea scale over time
7. Body mass index, airflow Obstruction, Dyspnoea and Exercise (BODE) index among the three groups at Day 14.

3 STUDY DESIGN

3.1 General study design

This is a phase IIa, two-part, randomised, multi-centre, multinational, double-blind, placebo-controlled, parallel-group study of 26 weeks duration in adult subjects with acute respiratory exacerbations in COPD. It will be conducted in approximately 100 centres in 12 countries (includes Europe [Germany, Italy, UK and some Central and Eastern European countries], Argentina and US). It is planned that approximately 320 subjects will be screened to randomise approximately 270 subjects, and expected that approximately 255 subjects will complete the study and follow-up. Only hospitalised subjects will be recruited.

[figure not shown]
Study is divided into 2 parts:

Acute Exacerbation Phase: from Day 1 (Randomisation day) until Day 14. Drug Administration will be done at days 1, 3 and 5.

Stabilisation Phase: requires subject evaluations at Weeks 8, 12 and 26.

The Study Flow Chart is presented in Figure 1.

Figure 1: Study Flow Chart

3.2 Randomisation and blinding

3.2.1 Randomisation

This is a double-blind and randomised study. Each patient will be randomised in a 1:1:1 ratio to receive 1 of 2 BCT197 treatment schedules or Placebo. At Visit 1 all eligible subjects will be randomised via Interactive Response Technology (IRT) to one of the treatment regimens. The investigator or his/her delegate will contact the IRT after confirming that the subject meets all the inclusion criteria and none of the exclusion criteria. The IRT will assign a medication number to the subject which will be used to link the subject to a treatment regimen and will specify a unique medication number for the package of investigational treatment to be dispensed to the subject. The randomisation number will not be communicated to the caller.

3.2.2 Blinding

Study Blinding is done to ensure that treatment assignment is unbiased and concealed from subjects and investigator staff. A subject randomisation list will be produced by ICON Biostatistics using a validated system that automates the random assignment of subject numbers to randomisation numbers. These randomisation numbers are linked to the different treatment regimens, which in turn are linked to medication numbers. A separate medication list will be produced using a validated system that automates the random assignment of medication numbers to packs containing the investigational drug.

3.2.3 Unblinding

Subjects, investigator staff, persons performing the assessments, and data analysts will remain blind to the identity of the treatment from the time of randomisation until database lock. Unblinding is permissible after database lock or in case of emergency only (with the exception of unblinded DMC staff/members - Refers to SAP Section 8.9 'Interim analysis'). Emergency treatment code breaks should only be undertaken when it is essential to treat the subject safely and efficaciously. Emergency code breaks are performed using the IRT.

Moreover, the randomisation codes associated with each subject will be disclosed to PK analysts who will keep PK results confidential until database lock.

3.3 Study treatments and assessments

[figure not shown]
Study is planned for 26 weeks duration in adult subjects with acute respiratory exacerbations in COPD and divided into two parts: Acute Exacerbation Phase and Stabilisation Phase. All subjects are planned to be treated with test product or placebo on [REDACTED] after randomisation. Subjects will be screened for up to 24 hours and will be followed daily in the first week, at days 10 and 14, and up to 8, 12 and 26 weeks (+/- 3 days) post-treatment. A total of 12 visits are planned for the two parts of the study.

Screening (Visit 1):

Subjects will be screened on the day that they present with an acute exacerbation (Day 1); there will be no separate Screening Visit as subjects will receive their first dose of study treatment within 24 hours of presenting with an acute exacerbation and fulfilling the study entry criteria. Subjects will be eligible only if their treatment (SoC) has been initiated less than 24 hours before Randomisation and dosing (Day 1). For screen failures, re-screening may take place 1 month after complete recovery from a previous acute exacerbation of COPD.

Day 1 to Day 14 – Acute Exacerbation Phase:

Subjects will undergo all safety and efficacy assessments on Day 1. Physical examinations, 12-lead electrocardiograms (ECGs), pulmonary function test (PFT; spirometry), and blood sampling for biomarkers will be done every day during the Acute Exacerbation Phase (Days 1 to 7, Day 10 and Day 14). It is expected that subjects will be hospitalised during Days 1-7. However, if a subject improves and is discharged prior to Day 7, the subject should return to the facility daily through to Day 7 and on Days 10 and 14 for completion of study assessments. The subject should receive a diary on Day 1 after Randomisation to document any occurrences of COPD and rescue medication use. Prior to hospital discharge, the subject should be reminded about the use of the diary and need to bring their diary to all visits.

Subjects randomised to the placebo arm will be administered two matching placebo capsules that are identical to the test product in appearance but contain no active treatment. The placebo should be taken orally with fluids on days 1, 3 and 5 after randomisation, preferably at the same time each day.

Weeks 8, 12 and 26 – Stabilisation Phase:

Subjects will return to the facility for 3 follow-up visits at Weeks 8, 12 and 26, at which time the required assessments/procedures will be done.

Rescue Medication:

All subjects will be treated as per institution SoC, in agreement with GOLD 2015 updated version for treating COPD exacerbations. Open-label corticosteroids and/or antibiotics may be administered at the investigator's discretion. Subjects will be permitted to use SoC short-acting bronchodilators as rescue medication on an 'as needed' basis during the study.

A detailed description of procedures and assessments to be conducted during this study is summarised in the Schedule of Study Assessments in Table 1 below (refers to study protocol Final V5.0).

Table 1: Schedule of Study Assessments

Visit	Acute Exacerbation Phase									Stabilisation phase			
	1	2	3	4	5	6	7	8	9	10	11	12	
	Screening ¹	Randomisation/ Baseline ¹ Day 1	Day 2	Day 3	Day 4	Day 5	Day 6	Day 7	Day 10 (± 1 day)	Day 14 (± 1 day)	Week 8 (± 3 days)	Week 12 (± 3 days)	Week 26 (± 3 days)
Written Informed consent	X												
Demographics	X												
Medical history including current medical conditions ¹⁷	X												
Smoking history	X												
Inclusion/exclusion criteria	X												
Full physical examination ^{2,15}	X	X	X	X	X	X	X	X	X	X	X	X	X
Vital signs ²	X	X	X	X	X	X	X	X	X	X	X	X	X
12-Lead ECG ^{3,4,7}	X	X	X	X	X	X	X	X	X	X			
Assessment of inflammation of cervix and vagina ¹⁶	X							X		X			
Pregnancy test ⁴	X										X	X	X
Clinical laboratory tests ^{2,5,6} (haematology, blood chemistry and urinalysis laboratory assessments)	X	X		X		X		X	X	X	X	X	X
PK assessment ⁷		X		X		X							
PFT (Spirometry)	X ^{9,13}	X ^{8,13}	X ⁸	X ⁸	X ^{8,14}	X ^{8,14}	X ^{8,14}						
Randomisation		X											
mMRC.		X						X		X	X	X	X

6MWT/BMI ¹⁰										X			
CRQ		X								X	X	X	X
Blood biomarkers ^{6,11}		X	X	X	X	X	X	X	X	X	X	X	X
Exploratory composite scale										X	X	X	X
EXACT-PRO		X	X	X	X	X	X	X	X	X	X	X	X
Study treatment													
Adverse events	X	X	X	X	X	X	X	X	X	X	X	X	X
Concomitant medications	X	X	X	X	X	X	X	X	X	X	X	X	X

- 1 Ideally subjects should be screened and randomised and dosed on the same day. There will be no separate Screening Visit as subjects will receive their first dose of study treatment within 24 hours of presenting with an acute exacerbation. Subjects will be eligible only if their treatment (SoC) has been initiated less than 24 hours before Randomisation and dosing (Day 1). For screen failures, re-screening may be performed 1 month after complete recovery from a previous acute exacerbation of COPD.
- 2 Vital signs and laboratory assessments should where feasible be performed before salbutamol intake. Height is to be measured at Screening only. Vital signs include body temperature, RR, pulse rate, blood oxygen (measured using a pulse oximeter), systolic and diastolic blood pressure. If Screening and Day 1 are on the same day and there is no medical indication, then vital signs and physical examination noted for Visit 1 do not need to be repeated. If Visit 1 is performed over different days, vital signs and physical examination should be repeated on Day 1 prior to randomisation only if the subject's condition has deteriorated.
- 3 12-lead ECG will be performed after 10 minutes rest. If the Screening Visit and Day 1 are on the same day and there is no medical indication then the ECG noted for Visit 1 does not need to be repeated. If Visit 1 is performed over different days, the ECG should be repeated on Day 1 prior to randomisation.
- 4 For women of child-bearing potential only. Urine dipstick pregnancy tests carried out by site at Screening and at all indicated visits; serum pregnancy tests will be performed centrally at the Screening and last visit only. Urine pregnancy tests will be used for the purposes of inclusion into the study due to the acute nature of the study.
- 5 Prior to entry into the study (Visit 1), clinical laboratory tests will be performed at a local laboratory to confirm eligibility for randomisation. These tests will also be performed by the central laboratory. If Screening and Day 1 are on the same day and there is no medical indication, then the clinical laboratory tests noted for Visit 1 do not need to be repeated. If Visit 1 is performed over different days, the local laboratory should repeat clinical laboratory tests on Day 1 if the subject's condition has deteriorated.
- 6 All blood samples are to be collected at least 6 hours after SABA intake whenever possible (times of sample collection and SABA intake must be recorded), 8 hours fasting (where possible) and after ECG and vital signs (including RR). INR and prothrombin time not required during the Stabilisation phase.
- 7 There will be sparse PK sampling in all subjects to be taken on any 2 of the 3 dosing occasions (Days 1, 3, or 5): one sample to be taken pre-dose, one sample taken 0-2 h post-dose, one sample taken 4-8 hours post-dose, and one sample no earlier than 12 hours post-dose. ECG will be taken at approximately the same time as with PK sample. ECGs should be taken before the PK sample.

A Symbol of Excellence

Statistical Analysis Plan (SAP)

- 8 Spirometry will be taken 'on bronchodilator' and ideally in the morning. For an individual spirometry should be taken at approximately the same time of day (during the acute phase \pm 1 hour and in the stabilisation phase \pm 2 hour window). Ideally this will be taken at least 1 hour after regular long acting bronchodilators and 30 minutes after short acting bronchodilator medication. Time of last short and long acting bronchodilators will be documented.
- 9 Spirometry at Screening should be performed 'on bronchodilator'. This will be taken after any regular long acting bronchodilator administration and 30 minutes after short acting bronchodilator medication.
- 10 Perform BMI and 6MWT at Day 14. BODE will then be calculated.
- 11 Please refer to the Laboratory Manual for clarification of whether the biomarker is to be analysed in either serum or plasma.
- 12 If the subject is discharged before Day 7, they will return to the hospital daily for assessment.
- 13 If screening and Day 1 occur on different days spirometry will be repeated on day 1 before dosing with study treatment and result obtained on day 1 may be used as baseline.
- 14 If historical spirometry data within last 12 months does not include pre and post SABA value this should be obtained during the stabilisation phase, for demographic purposes.
- 15 Physical examination at screening should include a minimum of chest, cardiovascular and abdominal examination. At all other time points a minimum of chest auscultation is required. Additional examination is at the discretion of the Investigator as indicated by the subjects' clinical condition.
- 16 A gynaecological history should be taken (from females only) with subjects specifically asked about vaginal bleeding, discharge or pain. Any new vaginal bleeding (other than normal menstruation), vaginal discharge or pain after dosing should be investigated by vaginal examination and any required specialist assessment.
- 17 Document in eCRF which symptoms of the acute exacerbation are present out of increased sputum, increased cough and increased dyspnoea.

Abbreviations: BMI = body mass index; BODE = Body mass index, airflow Obstruction, Dyspnoea and Exercise index; COPD: chronic obstructive pulmonary disease; CRQ = chronic respiratory questionnaire; ECG = electrocardiogram; eCRF: electronic case report form; EXACT-PRO: The EXAcacerbations of Chronic pulmonary disease Tool-Patient Reported Outcome; INR: international normalised ratio; mMRC = modified Medical Research Council; PFT = pulmonary function test; PK = pharmacokinetics; RR = respiratory rate; SABA = short-acting β_2 agonist; SoC: standard of care; 6MWT = 6-minute walking test

4 STUDY ENDPOINTS

4.1 Primary efficacy endpoint

The primary efficacy endpoint of this study is the change in FEV1 from baseline (pre-dose) to Day 7.

4.2 Secondary efficacy endpoints

The secondary efficacy endpoints of this study are:

1. Comparison of FEV1 on Days 3, 10, and 14
2. Normalisation evaluation of spirometry parameter (FEV1 and FEV1/FVC) response over time (performed daily from Days 1 to 7, 10, and 14, and Weeks 8, 12 and 26) compared with the most recent test performed within the last 12 months outside an exacerbation (pre-study FEV1 and FEV1/FVC value)
3. Time to improvement of 100 mL in FEV1 compared with Baseline versus placebo
4. Comparison of AUC of FEV1 over time among groups
5. Change in RR normalisation over time (performed daily from Days 1 to 7, 10 and 14) among groups
6. Change in RR on Days 3, 7, 10 and 14 among groups
7. Time to improvement based on EXACT-PRO total score
8. Comparison of AUC of EXACT-PRO over time among groups
9. Number of COPD-related deaths during the study
10. Number of moderate/severe COPD-related exacerbations during the study
11. Time to next moderate/severe COPD exacerbation
12. Change from baseline at each inter-visit period and over the entire period of the study in the average EXACT-PRO total score and domain scores
13. Number of times each subject required rescue therapy during the study
14. Time from hospitalisation admission until the subject is medically ready (COPD-related) for discharge
15. Nonlinear mixed effects pharmacokinetic/pharmacodynamic (PK/PD) models evaluating the relationship between BCT197 exposure and efficacy/safety endpoints.

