8.2 Secondary Objectives

The secondary objectives are to evaluate the efficacy and tolerability of two different dosing regimens of BCT197 added to SoC versus placebo added to SoC in treatment of an acute exacerbation of COPD requiring hospitalisation by measuring the following:

1. Comparison of FEV1 on Days 3, 10, and 14
2. Normalisation evaluation of spirometry parameter (FEV1, forced vital capacity [FVC], and FEV1/FVC) response over time (performed daily from Days 1 to 7, 10, and 14, and Weeks 8, 12 and 26) compared with the most recent test performed within the last 12 months outside an exacerbation (pre-study FEV1, FVC, and FEV1/FVC value)
3. Time taken to improvement of 100 mL in FEV1 compared to Baseline versus placebo
4. Assessment of AUC of FEV1 over time among groups
5. Respiratory rate (RR) normalisation over time (performed daily from Days 1 to 7, 10 and 14) among groups
6. RR at Days 3, 7, 10, and 14 among groups
7. Time to improvement based on EXACT-PRO total score
8. Assessment of AUC of EXACT-PRO over time among groups
9. Evaluate the number of COPD-related deaths among groups
10. Evaluate the number of moderate/severe COPD exacerbations (classified according to European Medicines Agency (EMA)/Committee for Medicinal Products for Human Use (CHMP) guidelines, refer to [Section 11.2.3](#)) over time among groups
11. Evaluate time to next moderate/severe COPD exacerbation
12. Change from Baseline at each inter-visit period and over the entire period of the study in the average EXACT-PRO total score and domain scores
13. Evaluate the use of rescue therapy during the study
14. Evaluate time from hospitalisation until subject is medically ready (COPD-related) for discharge
15. To characterise the PK of BCT197 in adults with COPD.

Safety and tolerability of BCT197

1. Evaluation of each treatment emergent adverse event (TEAE)/SAE (from first dose of study drug until study completion)
2. Evaluation of the incidence of pneumonia from first dose of study drug until study completion
3. TEAEs of special interest: rash, acneiform dermatitis, cervical/vaginal inflammation, headache, pruritus and liver enzymes (aspartate aminotransferase [AST], alanine aminotransferase [ALT], bilirubin)
4. Evaluation of vital signs and laboratory parameters
5. Evaluation of QTc intervals over time at Baseline, Day 1 to Day 7 (daily), Days 10 and 14
6. Quantitative sputum culture over Days 1 to 14 whenever sputum is collected for clinical purposes.

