11.2.1 Spirometry

Pulmonary function tests will be carried out under medical supervision in either a clinic or hospital and will be recorded using a computer-operated spirometer.

Lung function measurements and daily calibration of the spirometer will be done to the recommendations of the official Statement of the European Respiratory Society (ERS) and the American Thoracic Society (ATS). All sites will be provided with equipment and a central spirometry laboratory will be used. Investigator sites will be trained to the use of the system during the investigator meeting. All calibration reports should be printed and kept with the source study documents.

The specific procedures for the central spirometry will be provided to the investigator by the central spirometry company.

Forced Expiratory Volume in the 1st second in litres (FEV₁, L) and Forced Vital Capacity (FVC, L) will be recorded daily from Days 1 to 7 and on Days 10 and 14 during Part 1 of the study and at all visits of the Part 2 of the study. At either Week 8, 12, and 26 pre and post bronchodilator spirometry will be performed, for demographic purposes, if this information is not available from historical spirometry. This is additional to the 'on bronchodilator' spirometry, with the 'on bronchodilator' measurement being the priority.

The chosen value should not exceed the next by more than 150 mL. If the difference is larger, up to 8 measurements will be made and the highest value reported. The ratio FEV₁/FVC will be derived from this highest value of each parameter.

Predicted values will be automatically calculated with the demographics data recorded in the centralised system.

If more than one spirometry has been conducted within the 12 months before the study the most recent result, outside the exacerbation, will be used as the pre study value.

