13.4.2 Secondary Efficacy Endpoint(s)

Efficacy will be further assessed based on the following secondary endpoints:

1. Comparison of FEV1 on Days 3, 10, and 14
2. Normalisation evaluation of spirometry parameter (FEV1, FVC and FEV1/FVC) response over time (performed from Days 1 to 7, 10, 14, and at Weeks 8, 12 and 26) compared with the most recent test performed within the last 12 months outside and exacerbation (pre-study FEV1, FVC, and FEV1/FVC value)
3. Time taken to improvement of 100 mL in FEV1 compared to Baseline versus placebo
4. Comparison of AUC of FEV1 over time among groups
5. Change in RR over time (performed daily from Days 1 to 7, 10 and 14) among groups
6. Change in RR on Days 3, 7, 10 and 14 among groups
7. Time to improvement based on EXACT-PRO total score
8. Comparison of AUC of EXACT-PRO over time among groups
9. Number of COPD-related deaths during the study

10. Number of moderate/severe COPD-related exacerbations during the study
11. Time to next moderate/severe COPD exacerbation
12. Change from Baseline at each inter-visit period and over the entire period of the study in the average EXACT-PRO total score and domain scores
13. Number of times each subject required rescue therapy during the study
14. Time from hospitalisation until the subject is medically ready (COPD-related) for discharge
15. Nonlinear mixed effects PK/PD models evaluating the relationship between BCT197 exposure and efficacy/safety endpoints.

More details and the time points for collection are given in [Section 9.1.3](#) and in the Schedule of assessments ([Table 9-1](#)). A complete list of efficacy endpoints is given in [Section 11.2](#).

These secondary efficacy parameters will be assessed using the ITT population.

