7.1.4.2 FEV1 normalisation

FEV1 normalisation is achieved if FEV1 returns to a value $\geq 89\%^3$ of the most recent FEV1 value measured within the last 12 months outside an exacerbation (pre-study FEV1 value).

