7.1.4.3 FEV1/FVC normalisation

FEV1/FVC normalisation is achieved if FEV1/FVC returns to a value $\geq 89\%$ ³ of the most recent FEV1/FVC value measured within the last 12 months outside an exacerbation (pre-study FEV1/FVC value).

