The number and proportion of patients normalised for FEV1 (i.e. FEV1 returns to a value $\geq 89\%$ of the most recent FEV1 value measured within the last 12 months outside an exacerbation) at each visit will be reported by treatment regimen and Pearson's Chi-square test (or Fisher's exact test as appropriate) will be applied to compare normalisation rates at each visit between treatment regimens (two-sided test at 5% alpha level).

Moreover, a bar chart will be presented per treatment regimen for the normalisation of FEV1 at each visit showing the percentage of subjects normalised compared with the most recent test performed within the last 12 months outside an exacerbation.

A similar analysis will be used for:

- Normalisation of FEV1/FVC (i.e. FEV1/FVC returns to a value $\geq 89\%$ of the most recent FEV1/FVC value measured within the last 12 months outside an exacerbation) at each visit.

The timepoints to consider for these analyses are Days 1 to 7, Days 10 and 14, and Weeks 8, 12 and 26.

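### The SAP drops FVC from the protocol's spirometry-normalisation endpoint without declaring it, so no planned analysis asks whether FVC returns to its pre-study level

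*SAP*

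**What the plan says.** Protocol 13.4.2 gives secondary endpoint 2 as "Normalisation evaluation of spirometry parameter (FEV1, FVC and FEV1/FVC) response over time". The synopsis, 8.2 and 11.2 name the same three parameters, and 8.2 gives the reference as the "pre-study FEV1, FVC, and FEV1/FVC value".

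The SAP, which says it is based on protocol versions up to and including 5.0, names two. Its endpoint in 4.2 is "Normalisation evaluation of spirometry parameter (FEV1 and FEV1/FVC) response over time", and its objective in 2.2 shortens the reference to the "pre-study FEV1 and FEV1/FVC value". Two definitions follow. In 7.1.4.2, "FEV1 normalisation is achieved if FEV1 returns to a value" of at least 89% of the pre-study FEV1. In 7.1.4.3, "FEV1/FVC normalisation is achieved if FEV1/FVC returns to a value" of at least 89% of the pre-study ratio. SAP 8.6.3.2 compares FEV1 normalisation rates between regimens at each visit and repeats this for one further item, "Normalisation of FEV1/FVC (i.e. FEV1/FVC returns to a value" meeting the same 89% rule. FVC normalisation is neither defined nor analysed.

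SAP Section 9 declares three departures from the protocol: the per-protocol definition, the added per-protocol analyses and the steroid-dose window. None concerns FVC, and no amendment in Appendix A removes it. The data are collected. Protocol 11.2.1 says "Forced Vital Capacity (FVC, L) will be recorded daily from Days 1 to 7", and also on Days 10 and 14 and at every Part 2 visit.

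**The concern.** One of three named components of a pre-specified secondary endpoint is absent from the SAP, with no reason given. FVC is missing at every step, including the reference value in parentheses, so a single typing slip is an unlikely explanation. Section 9 declares and explains a change to an exploratory endpoint (steroid dose), so a change to a secondary endpoint belongs there too.

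If the SAP is followed as written, the study report will not say whether FVC recovered to its pre-exacerbation level in any arm at any visit. A reader comparing the report with the protocol would find a missing result and no explanation, and could not tell oversight from choice.

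**Working it through.** **No planned figure depends on this.** The only formal calculation in the documents is the sample size for the primary endpoint. A difference of 100 mL, SD 230 mL, two-sided alpha 0.05 and 80% power give 85 per arm by the t-based calculation (power 0.7999 at 84, 0.8046 at 85). Then 255/0.95 = 268.4, or 269, against the stated approximate 270. FVC does not enter it.

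**Does another planned analysis cover FVC recovery?**

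| | Protocol endpoint 2 | FVC ANCOVA, SAP 8.6.3.1 |
|---|---|---|
| Reference | Pre-study test, outside an exacerbation | Study baseline, during the exacerbation |
| Question | Has FVC returned to its usual level? | How far has FVC moved since entry? |
| Time points | Days 1–7, 10, 14; Weeks 8, 12, 26 (7 + 2 + 3 = 12) | Days 3, 7, 10, 14 (4) |

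The reference differs. Of the 11 time points after Day 1, 11 − 4 = 7 have no between-arm FVC comparison, including all three Stabilisation Phase visits.

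**Do the two retained measures imply FVC recovery?** Let a = FEV1 / pre-study FEV1 and b = FVC / pre-study FVC. The ratio as a fraction of its pre-study value is then a/b. The SAP rules are:

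- FEV1 normalised: a ≥ 0.89
- FEV1/FVC normalised: a/b ≥ 0.89

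The documents give no FVC rule. Assume b ≥ 0.89 for illustration:

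| a | b | a/b | FEV1 | Ratio | FVC (assumed rule) |
|---|---|---|---|---|---|
| 0.80 | 0.80 | 100.0% | no | yes | no |
| 0.75 | 0.84 | 89.3% | no | yes | no |
| 0.95 | 0.85 | 111.8% | yes | yes | no |
| 0.90 | 0.85 | 105.9% | yes | yes | no |
| 0.95 | 1.10 | 86.4% | yes | no | yes |

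In rows 1 and 2 both volumes are low. The ratio passes, but the separate FEV1 analysis correctly reads not normalised. In rows 3 and 4 FEV1 has recovered and FVC has not, and both retained measures pass.

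This is general. If a ≥ 0.89 and b < 0.89, then a/b > 1, so the ratio rule is always met. Under the assumed rule, no patient with recovered FEV1 and unrecovered FVC can be picked up by the SAP's two measures.

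**The case against.** The best defence is that little is lost. The FEV1 analysis, with its own definition, test and bar chart, already flags any patient whose two volumes are both low. FVC is not dropped from the SAP: 8.6.3.1 adds FVC comparisons by ANCOVA and descriptive FVC % predicted, in both the ITT and per-protocol populations. This is one component of one of 15 secondary endpoints in a Phase IIa study, with no multiplicity adjustment and with all analyses called exploratory (Protocol 13.5.1). The same section leaves full analysis detail to the SAP. All of this stands, and it limits the consequence. It does not make the omission a declared change, and it does not answer the protocol's question about FVC.

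Amendment 3, as summarised in Appendix A, says historical spirometry is needed for demography only, which might seem to explain the removal. It does not, because FEV1 and FEV1/FVC normalisation rely on the same historical test and are kept.

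A reader might also infer something stronger: that the ratio, left without FVC, counts unrecovered patients as recovered and so dilutes differences between arms, above all around Day 1. The documents do not support this. The ratio is one of the protocol's own components, and its results would be the same with FVC restored. The SAP builds no overall recovery status from it. Day 1 spirometry is pre-dose, so there is no treatment difference to dilute then. For later days the documents do not say how often the two volumes fall together.

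**Conclusion.** The discrepancy is real: the SAP removes FVC normalisation from objective, endpoint, definitions and analysis, and does not declare it. The consequence is limited to one unreported component of a secondary endpoint across 12 time points. The clinical profile left invisible is recovered FEV1 with FVC still below its pre-study level. How common that profile is cannot be estimated from the documents, and the percentages above are constructed illustrations. Calling FVC at 85% unrecovered rests on applying 89% to FVC, which is an assumption. The primary analysis, sample size and safety analyses are untouched, and no bias in arm comparisons has been shown. The point is worth correcting because it is cheap and restores the match with the protocol.

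**What to change.** Put FVC back in SAP 2.2 and 4.2. Add an FVC normalisation definition to 7.1.4, with a threshold the sponsor states and justifies. Using 89% would follow the FEV1 rule by analogy only, since the SAP takes that figure from an external reference and cites it for FEV1 and FEV1/FVC. Report FVC normalisation by visit in 8.6.3.2 beside FEV1 and FEV1/FVC, at the same time points and with the same tests.

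If leaving FVC out was deliberate, add it to Section 9 as a change from the protocol, with the reason.

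Restoring FVC costs one definition and one repeated table; declaring the removal costs one entry in Section 9. Neither needs new data.
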